## **PROTOCOL SUMMARY**

### **Background and Rationale**

We propose to ascertain intranasal oxytocin's effect on neural processes associated with the processing of reward stimuli. The neuropeptide oxytocin is best recognized for its effects on labor and lactation and has been well established to influence a wide-range of social behaviors including pair bonding and social interaction. Animal models demonstrate oxytocin's ability to influence social activity in part via its effects on neural circuits responsible for the processing of motivationally relevant stimuli. Whether oxytocin has similar effects in humans has not been tested. This research will utilize a state of the art neuroimaging technique, pharmacological functional magnetic resonance imaging (fMRI), in order to characterize the effects of intranasal oxytocin on brain activity elicited by motivationally relevant stimuli (social and monetary rewards).

Ongoing clinical trials are examining the use of intranasal oxytocin for the treatment of multiple psychiatric disorders including substance dependence, depression, and schizophrenia; disorders which reward system dysfunction appears to play a significant role. As such, it is important that we obtain a better understanding of the neurobiological effects this drug may have on reward circuitry functioning. To this end, in this study, we will examine healthy control participants and participants diagnosed with Alcohol Use Disorder (AUD).

### **Objectives and Endpoints**

Our primary objectives: examine the effects intranasal oxytocin administration has on brain activity elicited by social and monetary incentives using incentive delay tasks, which are designed to engage circuits that process natural and artificial rewards, in a group of healthy participants and participants diagnosed with AUD. This will allow us to establish whether intranasal oxytocin can influence brain activity associated with the processing of rewards and given the social nature of the hormone, whether oxytocin can influence such reward-related activity in a general sense or only when the reward has direct social relevance, and whether oxytocin produces similar alterations to reward-related activity in individuals diagnosed with AUD. Our study end will correspond to the final scan follow-up of our final participant.

### **Assessments**

Participants will be assessed at several different time points: first, at intake to collect preliminary information such as demographics, general history, drug use, social activity and trait measurements of mood, personality and well-being; then participants will be scanned using fMRI twice, once self-administering placebo and once self-administering intranasal oxytocin; participants will be followed-up with a phone call 24 hours following each scan to record and respond to any adverse events; finally, participants will be contacted for follow-up surveys 30, 60, and 90 days following their second fMRI visit.

### **Statistical Methods**

We will utilize standardized techniques to analyze the neuroimaging data obtained during the fMRI scans. Data will be analyzed using a widely used neuroimaging software package (e.g. Statistical Parametric Mapping, SPM).

## **1. INTRODUCTION**

### **1.1. Indication**

The proposed study will investigate the effects of intranasal oxytocin administration on neural activity associated with social and non-social motivation. Oxytocin is a well-known social and reproductive hormone demonstrated to have a variety of prosocial effects in humans including enhancing trust and generosity, improving positive communication, increasing eye gaze, and reducing anxiety [1-5]. Oxytocin is hypothesized to facilitate social behaviors via its modulation of reward networks [6]. With this study, we will characterize oxytocin's effects on the neural processing of reward in a healthy control population and in individuals diagnosed with Alcohol Use Disorder (AUD). We will utilize a noninvasive brain imaging technique, functional magnetic resonance imaging (fMRI), to assess brain activity while participants perform tests designed to engage neural circuits associated with the processing of social and non-social rewards.

### **1.2. Background and Rationale**

The brain's ability to appropriately identify the significance of everyday stimuli, assign a suitable incentive value and determine the appropriate action is critical for healthy functioning. When this system is disrupted, as it is with substance dependence, natural incentives, like social interactions with friends and family, may be devalued. Understanding the mechanisms that shape individual reactions to incentive stimuli is imperative to realizing the nature of the pathophysiological alterations that occur in many psychiatric disorders.

Recently, it has been suggested that the neuropeptide oxytocin, best known for its role in facilitating social and reproductive behaviors, may influence networks relevant to psychiatric illness. Animal work has indicated that oxytocin administration can induce dopamine release within the mesolimbic dopamine system [7,8] which has been hypothesized to be one mechanism by which oxytocin could impact incentive salience attribution to social stimuli (e.g. infants, conspecifics, mates) and to ultimately influence an organisms' drive towards such objects (e.g. [8-12]). Oxytocin's modulation of the neural circuits that control motivational processing does not appear to be limited to the social realm. Oxytocin can also alter central dopaminergic responses associated with non-social behaviors, including addictive behaviors (e.g. self-administration, tolerance, and dependence) (see review [13-18]). Although the animal literature suggests anatomical and functional interactions between oxytocinergic and motivational systems, there have been few human studies to date investigating the role of oxytocin in motivational processing.

#### **1.2.1. Study Rationale**

Studies on the neural effects of oxytocin administration in humans have been largely limited to brain studies examining emotional responsiveness, social cognition and trust [19-22]. This proposal seeks to establish, for the first time, the role oxytocin plays in the neural circuitries associated with reward and motivation in a human population. Though oxytocin has been primarily considered in the social realm, as indicated previously, some evidence suggests oxytocin can interfere with non-social processes (for review [13-18]). As such, we propose to characterize the effects of oxytocin on the neural processing of social and non-social rewards.

Several clinical trials are currently underway seeking to utilize oxytocin as a therapeutic agent to treat psychiatric illness (including autism, schizophrenia and substance use disorder (e.g.

[23,24])). As oxytocin is considered for this purpose, it is essential that we more completely characterize oxytocin's effects on systems relevant to psychiatric illness. Interestingly, recent research suggests oxytocinergic functioning may be altered in persons diagnosed with an alcohol use disorder (AUD). However, very little is known about how oxytocin administration may affect some of the key processes widely acknowledged to be disrupted in addiction -- particularly reward processes. As such, we propose to continue our work examining the influence intranasal oxytocin has on reward-related activity in control subjects and explore whether intranasal oxytocin produces similar alterations to reward-related activity in recently abstinent persons with AUD.

In order to achieve these research goals, we propose to employ a state of the art neuroimaging technique, pharmacological functional magnetic resonance imaging (pharmaco-fMRI). In this method, participants are given a drug prior to fMRI scanning which allows the investigation of drug effects on neural activity. This is an ideal method for studying neural modulation by drug and is safely done in healthy human populations.

### **1.2.2. Previous Human Experience**

Oxytocin was first synthesized in the laboratory in the 1950s and since that time has been primarily utilized for stimulation of milk ejection and uterine contraction [25]. Synthetic oxytocin is widely prescribed in the United States in injectable form and, prior to 1997, in intranasal form (the manufacturer of the intranasal form of synthetic oxytocin [trademark name Syntocinon®, NDA 012285], Novartis, let FDA approval of the product lapse, presumably for financial reasons: <http://www.fda.gov/ohrms/dockets/dockets/06p0068/06p-0068-cp00001-01-vol1.pdf> [26]). In 1968 the FDA, National Academy of Sciences and National Research Council concluded oxytocin administered intranasally was effective for the indication of initial milk letdown. Intranasal oxytocin is still marketed and prescribed throughout Europe for the stimulation of milk ejection (see review [27]).

Syntocinon® and other forms of synthetic intranasal oxytocin are commonly used agents in human research studies. As recently reviewed by MacDonald and colleagues, between 1990 and 2010, 38 randomized control trials were conducted which investigated the effects of intranasal oxytocin in humans [27]. A vast majority of the studies reviewed (79%) utilized Syntocinon® produced by Novartis and were conducted in healthy adults. In addition, in reviewing ongoing clinical trials (via [clinicaltrials.gov](http://clinicaltrials.gov)), we note there are currently over 25 active clinical trials utilizing intranasal oxytocin. In our review, we noted IND exemptions obtained from the FDA to utilize intranasal oxytocin in humans (i.e. #77,774, [name], University of North Carolina; #78,246, [name], University of Maryland).

### **1.2.3. Safety**

A review of the literature reports that short-term use of intranasal oxytocin administered in doses  $\leq 40$  IU, produces minimal side effects and adverse outcomes in healthy adults [27]. Intranasal oxytocin has also been safely used in multiple trials including persons diagnosed with psychiatric conditions including alcohol use disorder (AUD) and other addictive disorders [e.g. 43-44], schizophrenia [45-47], and depression [48]. In reviewing ongoing clinical trials (via [clinicaltrials.gov](http://clinicaltrials.gov)), we note 8 separate trials who have or are currently utilizing intranasal oxytocin in AUD populations (i.e. NCT02275611, NCT01212185, NCT02251912, NCT02058251, NCT02407340, NCT02711189, NCT02469259,

NCT02742532). However, Syntocinon® is not advised for use in women who are pregnant or planning to become pregnant (particularly as oxytocin is indicated for the induction and augmentation of labor). Also, it should not be given to patients with impaired hepatic or renal function and should not be administered to individuals with allergies to oxytocin or to the preservatives contained in the nasal spray. To reduce these risks, female subjects who are pregnant, nursing, or unable or unwilling to use effective methods of birth control during the study will be excluded from these studies. In addition, in reviewing PubMed, there was a single case-study indicating a significant adverse effect of long-term usage of intranasal oxytocin: in this case study, a 55-year old patient with obsessive-compulsive disorder self-administered oxytocin nasal spray multiple times a day, each day for 4 weeks and developed psychotic symptoms and decreased plasma sodium and osmolality [28]. In our protocol, participants will receive a single dose in a controlled setting. Finally, we will exclude participants with any acute or uncorrected medical illness, including participants who exhibit nasal obstruction or report using intranasally administered medications that cannot be stopped 48 hours prior to each scanning session.

#### **1.2.4. Risks**

There are some risks associated with the use of oxytocin. Frequencies are as follows: Very common ( $\geq 1/10$ ), common ( $\geq 1/100$  to  $< 1/10$ ), uncommon ( $\geq 1/1,000$  to  $< 1/100$ ), rare ( $\geq 1/10,000$  to  $< 1/1,000$ ), very rare ( $< 1/10,000$ ).

- Common: headache, tachycardia, bradycardia, nausea, vomiting
- Uncommon: arrhythmia
- Rare: rash, anaphylactoid reactions associated with dyspnoea, hypotension and shock
- Very rare: hypertension, one case of psychotic reaction and one case of seizure have been reported.
- Prolonged use of excessive doses with infusion of large volumes of fluid may cause water intoxication with hyponatraemia

Please refer to the attached document titled “Syntocinon® Novartis Pharmaceuticals” [29] provided by PharmaWorld and the document “Oxytocin (Systemic)” [30] obtained from <http://www.drugs.com/mmx/syntocinon.html?printable=1>, for more information on the safety and toxicology of oxytocin. Oxytocin is commonly given to induce or augment labor or to stimulate milk ejection, as such, Syntocinon will not be given to women who are pregnant, suspected pregnant, or breastfeeding.

In order to appropriately evaluate and respond to any potential adverse events, participants will self-administer the doses at the University of Utah while being monitored by study staff within the Imaging and Neuroscience Center. Female participants will be screened for pregnancy (urine test) prior to drug administration. Participants will be monitored by study staff at the University of Utah for approximately 2 hours following drug administration, given contact information in case of an adverse event, and contacted 24 hours following scanning to track any potential drug related effects.

#### **1.2.5. Dose Rationale**

A vast majority of the studies utilizing intranasal oxytocin have noted minimal side effects and

significant effects on mood, anxiety, and social behavior with a dose between 20-24 IU [27]. In keeping with this dosing, we propose to utilize a dose of 24 IU units delivered intranasally in a series of 6 puffs (3 puffs per nostril at 4 IU per puff) over 5 minutes.

## **2. STUDY OBJECTIVES AND ENDPOINTS**

### **2.1. Objectives**

Our main goal is to characterize the effects of intranasal oxytocin on brain activity associated with reward. We will utilize fMRI in order to assess changes in neural activity as a result of processing social and non-social reward stimuli. We will characterize this activity in healthy individuals as well as in individuals diagnosed with Alcohol Use Disorder. Our objectives are as follows:

#### **2.1.1. Primary Objectives**

- To determine the effect of intranasal oxytocin (Syntocinon®) on brain activity associated with social rewards using fMRI.
- To assess the effects of intranasal oxytocin (Syntocinon®) on the neural processing of non-social (i.e. monetary) rewards.
- To determine whether the neural responses to social cues and rewards are altered in recently abstinent persons with AUD.
- To determine whether the effect of intranasal oxytocin (Syntocinon®) on brain activity associated with social cues and rewards differs between control participants and recently abstinent persons with AUD.

### **2.2. Endpoints**

#### **2.2.1. Primary Endpoint**

- The primary endpoint will correspond to the final scan follow-up of the last participant. All group level analyses will be conducted at that time.

## **3. STUDY DESIGN**

This is a double-blind, placebo-controlled, randomized study of the effects of Syntocinon® on brain activity elicited during the processing of reward. Each participant will be studied twice using fMRI; once self-administering Syntocinon® and once self-administering placebo intranasally approximately 30 minutes prior to being scanned. Participants will be randomly assigned to self-administer either Syntocinon® or placebo first. Scans will be performed on separate days approximately 1-2 weeks apart.

Participants will be evaluated thoroughly at screening for eligibility and will only be entered into the study if they meet all inclusion criteria and none of the exclusion criteria.

88 participants are planned to complete the study (44 controls, 44 AUD). Total duration of the study is expected to be 60 months.

## **4. SUBJECT SELECTION**

### **4.1. Subject Recruitment**

Recruitment will take place through advertisement in the University and surrounding communities in newspapers, brochures, radio advertisements, social media advertisements (e.g., Facebook ads) and bulletin boards. We will also utilize the University of Utah's Enterprise Data Warehouse (EDW) and chart review to identify patients who appear to meet our inclusion criteria and are scheduled for treatment. For these potential participants, we will either contact the patient's physician/treatment team and ask for the opportunity to share information about the study with the patient or send a letter and brochure to these individuals prior to contacting them. Recruitment for the study will also include ResearchMatch.org, a national health volunteer registry that was created by several academic institutions to support recruitment for research studies. In order to target participants diagnosed with AUD, recruitment materials will be distributed to affiliated centers which assess and treat persons with AUD including the University Neuropsychiatric Institute (UNI), Assessment Referral Services (ARS), and Recovery Ways.

After an initial brief screen (typically conducted over the phone), subjects will undergo written informed consent procedures for study participation. Once an individual is considered suitable for study participation, the Mini-International Neuropsychiatric Interview will be administered to ensure study inclusion/exclusion criteria are met. Weight and height will be recorded and the body mass index computed.

### **4.2. Inclusion Criteria**

General Inclusion Criteria for All Participants:

- 18-45 years of age at the time of screening
- No current or past history of neurological illness
- No acute medical illness

Additional Inclusion Criteria for Control group:

- No current or past history of psychiatric illness, including substance use disorder (except nicotine)

Additional Inclusion Criteria for AUD group:

- Meet DSM-5 criteria for current moderate-to-severe AUD
- Abstinent from alcohol for 2-8 weeks prior to study enrollment
- Express a desire to achieve abstinence or to greatly reduce alcohol consumption

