### **4.3. Exclusion Criteria**

General Exclusion Criteria for All Participants:

- Known allergies to oxytocin or to preservatives in the nasal spray

- Participants unable to tolerate the scanning procedures or would be unfit for scanning purposes (e.g. metal implants, claustrophobic, unable to lie still for the duration of the scan)
- Female subjects who are pregnant, trying to become pregnant, or nursing
- Any current or past history of any serious medical or neurological illness
- Acute or uncorrected medical illnesses, including history of hepatic or renal dysfunction, hyponatremia, traumatic brain injury, atrophic rhinitis, recurrent nose bleeds, and cranial-surgical procedures (hypophysectomy).
- Abnormal MRI (except if due to technical factors)
- Participants reporting use of an intranasal medication that could not be stopped 48 hours prior to each scanning session
- Participants taking medications including any current treatment with antipsychotics, antidepressants, mood stabilizers, psychostimulants and psychostimulant appetite suppressants, hormone use (i.e. testosterone, DHEA), opioid drugs, isoniazid, glucocorticoids, centrally active antihypertensive drugs (e.g., clonidine, reserpine), or sedative hypnotic medications (e.g. benzodiazepines, barbiturates, within 1 week prior to study enrollment).
- Unable to comply with study procedures or protocols

Additional Exclusion Criteria for Control group:

- Any reported current (within the last 2 months) use of any category of illicit drugs

Additional Exclusion Criteria for AUD group:

- History of, or current, psychotic disorder, antisocial personality disorder, or bipolar disorder
- Concurrent posttraumatic stress disorder
- Dependence (moderate to severe) to any other substance within the last 2 months other than alcohol or nicotine

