## 6.11. List of Questionnaires & Surveys

### *Intake*

#### Mood/Anxiety

- Patient Health Questionnaire (PHQ-9, v3) (2-3 minutes)
- Adverse Childhood Experiences (ACE, v3) (5 minutes)

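### Controls must be free of any lifetime psychiatric illness but the AUD group may have depressive or anxiety disorders, so an Objective 3 group difference cannot be attributed to AUD alone

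*Protocol*

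**What the plan says.** **Controls.** Section 4.2 asks for "No current or past history of psychiatric illness, including substance use disorder (except nicotine"). Nicotine is the only exception, and the rule covers the past as well as the present.

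**AUD group.** Section 4.3 lists three exclusions: "History of, or current, psychotic disorder, antisocial personality disorder, or bipolar disorder"; "Concurrent posttraumatic stress disorder"; and "Dependence (moderate to severe) to any other substance within the last 2 months other than alcohol or nicotine". Depressive and anxiety disorders, current or past, are not on the list.

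**Both groups.** Section 4.3 also excludes "Participants taking medications including any current treatment with antipsychotics, antidepressants, mood stabilizers" and several other drug classes. This removes people on treatment but not those with untreated or remitted illness.

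**Link to the outcome.** The Protocol Summary describes oxytocin trials in "multiple psychiatric disorders including substance dependence, depression, and schizophrenia; disorders which reward system dysfunction appears to play a significant role".

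**Use of the group contrast.** Objective 3 in section 2.1.1 is "To determine whether the neural responses to social cues and rewards are altered in recently abstinent persons with AUD". Section 8.2.2 predicts lower anticipation responses in the nucleus accumbens, insula and anterior cingulate of the AUD group. Objective 4 compares the oxytocin effect between the two groups.

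**Adjustment.** Section 8.2.3 plans regression and ANCOVA for variables of which age is the example, and mentions attachment and sociability measures as a way to explain variation. The M.I.N.I. (sections 4.1 and 6.10) and the "Patient Health Questionnaire (PHQ-9, v3") in section 6.11 are collected at intake. Neither is tied to the Objective 3 or 4 comparison.

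**The concern.** Only the order of oxytocin and placebo is randomised (sections 3 and 5.1). Whether a participant is a control or an AUD case is observed, so the Objective 3 contrast is only as clean as the eligibility rules make it. These rules admit depressive and anxiety disorders in one group and forbid them in the other.

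For depression, the protocol itself supplies the reason to expect an effect on the outcome. A lower reward response in the AUD group is the result predicted for AUD. It is also what one-sided admission of depression could produce, so the predicted result would not separate the two explanations. At stake is how one of the four primary objectives may be worded when it is reported, and possibly a second.

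**Working it through.** **1. Criteria side by side**

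| Condition | Control | AUD |
|---|---|---|
| Depressive disorder, current (not on a barred drug) or past | excluded | admitted |
| Anxiety disorder, current (not on a barred drug) or past | excluded | admitted |
| PTSD, past only | excluded | admitted |
| Other substance disorder, mild or more than 2 months ago | excluded | admitted |
| Psychotic, bipolar or antisocial personality disorder | excluded | excluded |
| Current PTSD | excluded | excluded |

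Controls have no psychiatric diagnosis by design. Adjusting for diagnosis in a model of both groups would therefore have no overlap to work with.

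**2. The plan's own figure.** Section 8.1 states at least 90% power for 0.77 SD with 44 subjects at one-sided 0.005. A one-sample or paired t test with n = 44 gives 99.0%. A two-sample test with 44 per group gives 83.3%. Neither returns 90%, and the software's variance inputs are not given. This does not decide the present point. It supplies the group size, the threshold and the effect size used below.

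**3. Bias under Objective 3.** Let *p* be the share of the AUD group with a comorbid disorder and *δ* its effect on the contrast in SD units. Controls contribute zero. With no true AUD effect, the expected group difference is *p* × *δ*. The documents give neither quantity. Assume *p* = 0.20 to 0.40 and *δ* = 0.3 to 0.8:

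- low: 0.20 × 0.3 = 0.06 SD
- middle: 0.40 × 0.5 = 0.20 SD
- high: 0.40 × 0.8 = 0.32 SD, which is 0.32 / 0.77 = 42% of the planning effect

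**4. False-positive chance.** Two-sample t test, 44 v 44, df = 86, one-sided 0.005, critical value 2.634. The noncentrality is *d* × √(44/2).

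| Spurious *d* | Noncentrality | Chance of a significant difference |
|---|---|---|
| 0 | 0 | 0.5% |
| 0.06 | 0.28 | 1.1% |
| 0.20 | 0.94 | 4.9% |
| 0.32 | 1.50 | 13.5% |

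Allowing for the extra variance that the mixture adds to the AUD group lowers the last figure to 12.4% and leaves the 1.1% unchanged.

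**5. Objective 4.** The drug effect is the difference between each person's oxytocin and placebo scans. If comorbidity adds a constant *c* to both, then (O + *c*) − (P + *c*) = O − P, and the constant drops out. A bias remains only if comorbidity changes the oxytocin response itself by some amount *γ*, and it then equals *p* × *γ*. The documents give no figure for *γ*, so the numbers in steps 3 and 4 do not carry over.

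**6. Precision of the remedy.** Omitting 20-40% of 44 leaves 44 × 0.80 ≈ 35 to 44 × 0.60 ≈ 26 AUD participants against 44 controls. The standard error is √(1/n + 1/44) SD: 0.213 with 44, 0.226 with 35 and 0.247 with 26, an increase of 6% to 16%. Power for 0.77 SD at one-sided 0.005 falls from 83% to 77% and 68%.

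**The case against.** The strongest reply is that Objective 3 asks whether responses are altered in people with AUD, not whether AUD acts in isolation. Section 8.2.2 even counts social impairments, which it calls common in substance dependence, among the reasons to expect a larger oxytocin effect. On that view comorbidity belongs to the population of interest, and removing it would narrow the target. This stands as a reason to leave the entry criteria alone. It does not license a conclusion about AUD alone.

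A second reply is that sensitivity analyses usually belong in the SAP, which is not shown. That is fair for the analysis detail, and a SAP may already provide for it. But the confounding comes from eligibility rules fixed in the protocol, and section 8.2.2 frames the expected difference in terms of AUD.

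Three stronger readings are tempting, and the documents support none of them:

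- *The difference cannot be attributed to AUD at all.* The size depends on an unknown comorbidity share. The exclusions for psychotic, bipolar and antisocial personality disorder, current PTSD and psychotropic medication also limit it. At the low end the effect is negligible.
- *Objective 4 is biased in the same way.* A fixed shift cancels within person. Section 8.2.2 suggests that social impairment may increase the benefit from oxytocin, which offers a route for effect modification. No passage says so of depression or anxiety disorders.
- *Section 8.2.3 adjusts for age only.* Age is an example in an open list, and attachment and sociability measures are mentioned as well.

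Two limits also stand. The protocol's link to reward dysfunction names depression and not anxiety, so the case for anxiety rests on the asymmetry alone. The 0.005 threshold belongs to the ROI power calculation; none is stated for the whole-brain analysis, and a stricter one would lower the percentages.

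**Conclusion.** The point holds in a limited form. The psychiatric criteria differ between the groups, and the protocol ties at least one of the conditions admitted on one side to the outcome. It names no step that separates that condition from AUD. A group difference under Objective 3 is therefore attributable to AUD together with its admitted comorbidity, not to AUD alone. Objective 4 shares the problem only if comorbidity modifies the oxytocin response, which the documents neither show nor rule out. The oxytocin effect within each group is a randomised within-person contrast and is unaffected.

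The size cannot be known from the documents. The range in the working, from negligible to about two fifths of the planning effect, rests on an assumed prevalence, an assumed effect, no true AUD effect and the ROI threshold. It shows that the bias could matter, not that it will.

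**What to change.** Keep the entry criteria and the primary analysis. In section 8.2.2:

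1. For Objective 3, prespecify a sensitivity analysis of the group contrast that omits AUD participants with a depressive or anxiety disorder on the M.I.N.I. State whether past as well as current diagnoses count. Report its estimate and confidence interval beside the primary result. Do the same for Objective 4 as a supportive analysis.
2. Word the primary conclusion as AUD with its admitted comorbidity versus psychiatrically healthy controls. This also covers the past PTSD and the mild or earlier substance disorders that the subset analysis does not remove.
3. Treat adjustment for PHQ-9 as optional and exploratory, since it may remove part of a true AUD effect.

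Set no pass/fail rule for attribution; the reader should compare the two estimates with their intervals.

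The cost is one further analysis of data already scheduled at intake. The downside is precision: with about 26-35 AUD participants left, the interval is roughly 6-16% wider, so a smaller or non-significant subset result would not by itself show that comorbidity explains the difference.
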